### **8.7.4 Pooled MLS Predose Flecainide Cohort (Cohort 4)**

This Cohort includes all subjects in the study population (i.e., safety, mITT etc.) who are part of the Pooled MLS Cohort (Cohort 2) and have flecainide present in their predose PK sample (i.e., flecainide plasma concentrations > 0 ng/mL). This Cohort will be referred to as Cohort 4.

## **8.8 Patient-Led (PLS) Population**

The PLS analysis will include all subjects who signed Informed Consent for the Part C Patient-Led Study (i.e., the PLS Population of Consented Subjects). All further PLS Populations (safety, mITT, etc.) will be based on the PLS Population of Consented Subjects and will use the population definitions described in Sections 8.2 through 8.6.

A consort diagram will present the number of subjects included in each PLS Population (i.e., safety, mITT etc.); however due to the small number of PLS subjects who received study drug, all PLS data will be presented for the overall study populations (i.e., no Cohort analysis).

All PLS subjects were previously successfully treated with inhaled flecainide earlier in Part A, B or C of the MLS.

**FLE-002 (INSTANT) – Final Analysis****Statistical Analysis Plan****9 Statistical Methods**

Statistical programming and analyses will be performed using established statistical methods.

The study data will be reported using tables, figures, and data listings. Descriptive statistical methods will be used to summarize the data from this study.

Continuous variables will be descriptively summarized using number of subjects (n), mean and standard deviation (SD), additionally coefficient of variation (CV (%), as appropriate), median, minimum, maximum, and, as appropriate, geometric mean may be reported. If required, a 95% two-sided confidence interval will be reported for the mean, using Student's t-distribution.

Categorical variables will be descriptively summarized by presenting the number (frequency) and percentage in each category. If required, a 95% exact two-sided confidence interval will be reported for each proportion using the binomial distribution.

A selection of data collected during the study will be included in data listings. Unless otherwise noted, the data will be sorted by subject identifier, and (where applicable) by date within each subject identifier.

The statistical analyses will be conducted using SAS® System version 9.3 or higher. Validation will be performed in accordance with applicable Cardialysis SOPs.

**9.1 Patient Disposition, Demographic and Baseline Characteristics**

Patient disposition will be presented for all subjects who signed Informed Consent, i.e., Population of Consented Subjects. The number of subjects who completed the study and discontinued from the study will be summarized. The reasons for early discontinuation at any time in the study will be described by dose cohort. Screen failures are defined as subjects who signed Informed Consent but were not enrolled (randomized or allocated).

Disposition, demographic and baseline characteristics data, including age, gender, race, ethnicity, etc. will be summarized in tables for each MLS population and cohort as described in Section 8, but no statistical testing will be performed.

Medical history and AEs will be coded using the Medical Dictionary for Regulatory Activities (MedDRA) (version 23.1 or higher) for the study period. Medical history and AEs may be summarized in tables and will be presented in data listings.

Prior and concomitant medications will be coded using the World Health Organization (WHO) Drug Dictionary (version WHO September 2019 or later). Prior and concomitant medications may be summarized in tables and will be presented in data listings.

A separate consort diagram will be provided for the pooled analysis (Part A, part B and Part C MLS) and for Part C PLS.

**9.2 Specification of Analyses****9.2.1 Primary efficacy endpoint**

The primary efficacy endpoint is the proportion of subjects whose AF converted to SR by inhaled flecainide within 90 minutes after initiation of dosing.

## FLE-002 (INSTANT) – Final Analysis

## Statistical Analysis Plan

Analysis is performed for the mITT population. A Subject meets the endpoint if conversion occurred within 90 minutes after initiation of dosing without the use alternative medication (e.g., IV flecainide and propafenone) or procedures (e.g., ECV). If a subject's conversion status is unknown, then the analysis will assume that the subject did not convert.

The percentage is calculated as:

$$p = 100 * (\text{number of converted subjects} / \text{number of subjects in mITT population})$$

A 90% exact binomial confidence interval will be calculated for the percentage.

No formal testing will take place. Analysis will not be performed for the PLS population.

### 9.2.2 Secondary efficacy endpoints and other assessments analyses

#### 9.2.2.1 *The proportion of subjects with $C_{max}$ values $\geq 200\text{ng/mL}$ (e.g., 200, 300, 400, and 500 $\text{ng/mL}$ ) post inhalation with inhaled flecainide (excluding plasma levels associated with IV flecainide infusion) whose AF converted to SR by inhaled flecainide within 90 minutes after initiation of dosing*

This endpoint is reported for the mITT population.

The definition of conversion is identical as used for the primary efficacy endpoint meaning that If subject converts due to alternative medication (e.g., IV flecainide and propafenone) or procedures (e.g. ECV) patient fails the endpoint.

For the purpose of this study,  $C_{max}$  is defined as the peak plasma level of flecainide prior to administration of any alternative pharmacological agent (e.g., IV flecainide).

The endpoint will be reported as percentages for eight different  $C_{max}$  cut-off values as will the corresponding 95% Clopper-Pearson two-sided Confidence Intervals.

The first percentage measures the conversion rate within 90 minutes after initiation of dosing, regardless of PK values, implying a  $C_{max}$  cut-off value of 0.

$$P_1 = 100 * (\text{number of converted subjects} / \text{number of subjects in mITT population})$$

The other seven percentages measure the conversion rate within 90 minutes after initiation of dosing using a specific cut-off value of  $C_{max}$ . In order to be included in the analysis for subject sufficient information must be available to calculate  $C_{max}$ . The proportions are defined as:  $100 * \text{Numerator} / \text{Denominator}$ .

Proportion	Numerator: number of converted subjects with:	Denominator: Number of subjects with
$P_2$	$C_{max} < 200$	$C_{max} < 200$
$P_3$	$C_{max} \geq 200$	$C_{max} \geq 200$

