In both parts of the FLE-001 study, inhaled flecainide displayed a rapid distribution phase lasting $\approx 10\text{-}15$ minutes, with an estimated $t_{1/2\alpha}$ of 3.5-4.2 minutes and elimination $t_{1/2\beta}$ of 9-12 hours. The distribution phase and elimination half-life were independent of the doses of inhaled flecainide whereas the C_{max} and AUC_{last} were dose-dependent. In the cross-over study, the distribution phase and elimination half-life were nearly identical for intravenous infusion and inhalation: 4.7±01.4 min and 10.0±1.8h for intravenous, and 4.3±1.5 min and 10.1±2.0h for inhalation. The relevancy of this finding is linked to the fact that flecainide given via IV at the approved dose of 2 mg/kg is an established agent for acute pharmacological cardioversion of recent onset AF (efficacious and safe dose).

In the FLE-001 cross-over study, a within subject comparison of the PK, PD, safety and tolerability of 30 mg eTLD of flecainide given via oral inhalation was made with that of a 10 min IV infusion dose of 2 mg/kg of flecainide (\approx 150 mg). To directly compare the PK profiles of flecainide given via IV infusion and oral inhalation, the mean \pm SD plasma flecainide

[figure not shown]
INSTANT Study Clinical Study Protocol

Study no. FLE-002

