Therefore, inhaled flecainide at eTLD \geq 30 mg was found to yield venous plasma flecainide concentrations and cause QRS interval prolongation within the range, albeit in the lower end of the range, reported to convert AF to SR by IV flecainide⁴²⁻⁴⁴. Based on the PK and PD of flecainide reported in the literature, inhaled flecainide at eTLDs \geq 30 mg are considered likely to be effective in converting recent-onset AF to SR within minutes of administration; the 30 mg dose was used as the starting dose for the INSTANT study.

The FLE-003 study consisted of two Parts. Part 1 of the study was a single-center, double-blind, randomized, placebo-controlled design. A total of 21 subjects were enrolled in Part 1 (of 2) with ascending eTLDs of 75 mg (6 subjects: 2 placebo and 4 IH flecainide) and 90 mg (15 subjects: 3 placebo and 12 IH flecainide). A dose-dependent increase in plasma flecainide concentrations was observed for the 75 and 90 mg eTLDs, along with a transient (~ 3 minutes) increase in QRS and PR interval durations. C_{max} values reported for the 75 mg and 90 mg doses were 301 ng/mL and 347 ng/mL, respectively; whereas, the mean maximum change in QRS interval were generally small and ranged up to 8 msec at the 90 mg eTLD. Part 2 was an exploratory, openlabel study, in which 6 subjects (5 from Part 1 and 1 naïve subject received 1 or 2 doses of inhaled flecainide. The main goal was to compare the PK of a 90 mg eTLD given to the same subjects at two compressed air flow rates. There were no significant differences in C_{max} values following inhalation of the 90 mg dose using compressed air pressure of 8 L/min (340 ng/mL) or 5 L/min (313 ng/mL) in the same 5 subjects, indicating no clear trend for effect of compressed air flow rate on C_{max} (or any PK parameter). Overall, inhaled flecainide at eTLDs of 75 and 90 mg was safe and well tolerated. The most frequently reported adverse events were headache, oropharyngeal pain, and throat irritation; all adverse events were mild and resolved spontaneously, and no serious adverse events were reported.

Additional information on the results of the Phase 1 studies conducted are provided in Section 5 of the IB⁴¹.

The results of the Phase 1 studies warrant further development of inhaled flecainide, i.e., justify a Phase 2 study in patients with recent-onset paroxysmal episodes of AF. The rationale and objectives for the development of this route of administration of flecainide are described below.

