- 9. Site staff shall closely observe the subject during inhalation to ensure that the subject only inhales and exhales through the mouth.
- 10. Once the inhalation rhythm is established, the subject should not remove the mouthpiece of the inhaler from the mouth during the entire inhalation time. If the subject removes the mouthpiece of the inhaler from their mouth for any reason/cause (e.g., cough, excessive saliva, etc.) and the inhalation is interrupted for > 30 seconds, then the inhalation time may be extended by the duration of the interruption if conversion of AF to SR is not achieved during inhalation. During the entire inhalation procedure, the nurses shall remain vigilant and ready to assist the subjects to successfully complete each inhalation period.
- 11. Once conversion of AF to SR is observed on telemetry, the time of the observation should be recorded as the time of conversion; however, the subject must continue dosing for at least 1 minute to confirm that SR is stable. If SR does not remain stable

INSTANT Study Clinical Study Protocol

Study no. FLE-002

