⁶ A diagnostic echocardiogram using a Sponsor-provided handheld portable ultrasound device (HHE) is performed during screening to evaluate for exclusionary structural heart or functional abnormality for US subjects who do not already have a standard diagnostic echocardiogram (including LVEF) within 6 months prior to screening, or for EU subjects who have specifically consented to the HHE Sub-Study.

⁷ Triplicate ECGs are extracted from the AECG by the ECG Core Laboratory after data are transmitted by the site. ECGs are extracted within 5 minutes after the scheduled time point or up to the next scheduled time point, whichever comes first.

⁸ Just before starting inhalation (IH) regimen.

⁹ Heart rate, systolic and diastolic blood pressure, respiratory rate (breaths/min) and SpO2. Body temperature is recorded at screening only. When time-points coincide for blood draws and vital signs, procedures are performed in that order.

¹⁰ Record the start and stop times for each inhalation stage. If a subject's AF converts to SR within the first inhalation stage, then the break and the second inhalation stage will not take place.

 $^{^{\}rm 11}$ The subject shall be seated upright after the –30-minute time point assessments are completed.

¹² Refer to Section 9.2 B.

¹³ After 90 minutes post dose and prior to discharge, subjects whose AF is converted to SR by study drug will be asked questions related to their treatment satisfaction (refer to Section 7.4 B).

Study no. FLE-002

Version 8.0 EU-1 Page: 114 of 117

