**6.2.5.1 Pharmacokinetic (PK) assessment(s)**

## **FLE-002 (INSTANT) – Final Analysis**

## **Statistical Analysis Plan**

Whole blood samples of about 4.0 mL are collected for measurement of plasma concentrations of flecainide acetate components. PK sampling occurs only over a 90 min period on Day 1 (day of dosing).

For all reported subjects (i.e., Part A (2\*60 mg FlecIH-103 subjects) Part B, and Part C MLS) sample collection times are as follows:

1. Pre-dose inhalation –  $T_{Pre}$  (any time up to 45 minutes prior to dosing and after treatment assignment)
2. During dose regimen administration –  $T_{between\ admin}$  (in the 1-minute break in between inhalations), if applicable
3. At the time of conversion to SR –  $T_{SR}$ . A PK sample should be taken at SR regardless of method of conversion. If conversion is, for example, by ECV, the PK sample should be taken at the earliest time feasible.
4. After administration of study drug regimen is complete –  $T_x$  (1, 3, 10, 30, 60 and 90 minutes post dose).

All available information will be reported. The analysis will be performed for the PK population (refer to SAP section 8.4).

For the subjects in Part C PLS who received study medication only three samples are collected: pre-dose, at 3 minutes post end of dose and at 90 minutes post end of dose, additionally at the time of conversion to SR –  $T_{SR}$  a PK sample should be taken regardless of method of conversion. If conversion is, for example, by ECV, the PK sample should be taken at the earliest time feasible.

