**FLE-002 (INSTANT) – Final Analysis****Statistical Analysis Plan****8.5 Modified Intention-To-Treat Population (mITT)**

The modified ITT population includes all enrolled subjects who completed the full assigned dose of study drug and were in AF at the time of start of the inhalation of the study drug. Subjects whose AF converted to SR prior to completion of the assigned full dose of study drug will also be included in the mITT population.

Completing the assigned dose of study medication in accordance with the protocol (i.e., dose/inhale to conversion) is defined as completing both inhalation stages, for a total dose of 120 mg eTLD (2 x 60 mg eTLD), OR completing the dosing early due to conversion of AF to SR. All subjects who converted prior to completion of the assigned 120 mg dose of study medication will be included in the mITT population, regardless if they stopped dosing or continued.

The mITT population will be used to evaluate all primary and secondary efficacy endpoints. Population includes Part A, Part B and Part C MLS subjects receiving 120 mg FlecIH-103.

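### The conversion-by-Cmax table uses mITT, where a dose shortened by conversion can appear only as a success, so the <200 ng/mL row generally reads too high and no full-dose check is planned

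*SAP*

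**What the plan says.** SAP 9.2.2.1 gives eight percentages. P1 is the overall rate. Of the rest it says "The other seven percentages measure the conversion rate within 90 minutes after initiation of dosing using a specific cut-off value of" Cmax: P2 is conversion among subjects below 200 ng/mL, and P3 to P8 are conversion among subjects at or above 200, 300, 400, 500, 600 and 700. On population it says "This endpoint is reported for the mITT population". Cmax (SAP 3.5) is the observed peak before any alternative drug, with no adjustment for dose received.

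The regimen is inhale-to-conversion. Footnote 10 to Protocol Table 4 (17.4.3) says that if AF "converts to SR within the first inhalation stage, then the break and the second inhalation stage will not take place". Protocol 5.3.4 B adds that after conversion is seen "the subject must continue dosing for at least 1 minute to confirm that SR is stable".

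SAP 8.5 defines mITT as subjects in AF at the start who took the full dose, with one exception: "All subjects who converted prior to completion of the assigned 120 mg dose of study medication will be included in the mITT population", whether or not they stopped inhaling. A non-converter who stops early is therefore out.

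SAP Table 1 (section 8) assigns efficacy to mITT only. Neither document plans a full-dose version of P2–P8. Protocol 10.2.3 B refers to a separate PK/PD plan, which was not available to check.

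**The concern.** The outcome partly determines the exposure row. Early conversion cuts the dose, a smaller dose lowers Cmax, and the subject can move from a higher row to a lower one as a success. The matching failure, a non-converter with a short dose and low Cmax, is removed by the mITT definition. Part of any difference between P2 and P3 is then produced by the stopping rule and the population definition.

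A smaller effect runs the other way. SAP 6.2.5.1 says "A PK sample should be taken at SR regardless of method of conversion", so converters have an extra chance to catch a high value.

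This is the first-listed secondary efficacy endpoint, and the protocol (7.3 C) treats 200 ng/mL as therapeutic dosing. A reader will compare P2 with P3 to judge whether reaching that level matters. The likely error is to understate exposure-response.

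**Working it through.** The SAP gives no expected figure for this table, so there is nothing of the plan's to reproduce except the Part A rate: 13/27 = 48% (Protocol 1.4).

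**Direction.** Let the rows under full dosing be c/n (<200) and C/N (≥200). If e early converters fall below 200:

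- P2 becomes (c+e)/(n+e), which is never below c/n.
- P3 becomes (C−e)/(N−e), which is never above C/N.

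This ignores the extra sample at SR. As an illustration, take 27 subjects, 13 converters, and full-dose rows of 3/6 and 10/21:

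| e | P2 | P3 |
|---|---|---|
| 0 | 3/6 = 50.0% | 10/21 = 47.6% |
| 1 | 4/7 = 57.1% | 9/20 = 45.0% |
| 2 | 5/8 = 62.5% | 8/19 = 42.1% |
| 3 | 6/9 = 66.7% | 7/18 = 38.9% |

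**Is 200 within reach of a shortened dose?** Protocol 1.2.2 says Cmax "values reported for the 75 mg and 90 mg doses were 301 ng/mL and 347 ng/mL, respectively", and gives 102 ng/mL for 30 mg inhaled. Scaled to 60 mg:

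- 301 × 60/75 = 241
- 347 × 60/90 = 231
- 102 × 60/30 = 204

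A typical subject who receives one stage sits just above 200, so those with below-average exposure, or who stop during stage one, fall under it.

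**Size, by simulation** (1,000,000 subjects per scenario).

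Inputs from the documents:
- 13 of 29 convert and 2 of 29 are partial-dose exclusions (assumed non-converters), giving 48% in mITT.
- Dosing is 3.5 + 1 + 3.5 minutes and continues 1 minute after conversion.
- One full-dose median is 465 ng/mL, from 301 × 120/75 = 482 and 347 × 120/90 = 463.

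Inputs assumed:
- an alternative median of 350 and a lognormal CV of 60%;
- 10, 25 or 40% of converters converting during dosing, uniformly from 0.5 to 8 minutes.

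Two models for Cmax after a short dose:
- *Proportional:* Cmax proportional to inhaled time.
- *Distribution:* Protocol 1.2.2 says "inhaled flecainide displayed a rapid distribution phase lasting" about 10–15 minutes, with half-life 3.5–4.2 minutes; 3.85 is used, with the actual sampling times and the SR sample. One stage then gives 1/(1 + 2^(−4.5/h)) of the full peak: 71%, 69% and 68% for h = 3.5, 3.85 and 4.2.

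Results with no true relation (about 48% in every row):

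| Converters converting during dosing | P2, proportional | P3, proportional | P2, distribution | P3, distribution |
|---|---|---|---|---|
| 10% | 53–56% | 47.1–47.5% | 50–52% | 47.8% |
| 25% | 58–65% | 45.8–46.4% | 53–57% | 47.1–47.6% |
| 40% | 62–70% | 44.3–45.3% | 56–60% | 46.4–47.1% |

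If conversions during dosing come only from minute 5.5, the P2−P3 gap is +0.4 to +2.7 points (proportional) or −0.5 to −2.8 (distribution, because of the SR sample).

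With a true relation (odds ratio 2 per doubling of full-dose Cmax), the true P3−P2 gap of 23–26 points becomes:

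| Converters converting during dosing | Proportional | Distribution |
|---|---|---|
| 10% | 15–17 | 20–22 |
| 25% | 3–8 | 16 |
| 40% | −6 to +1 | 11–13 |

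**Row size.** Under these distributions 6–16% of mITT lies below 200: 3–8 of the 27 Part A plus 25 planned Part B subjects, with an unknown number from Part C. A row of 4/8 (50%, 95% CI 16–84%) becomes 6/10 (60%) if two shortened-dose converters drop into it.

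**Does the proposed set remove the artefact?** Among subjects still in AF after completing both stages, with scheduled samples only and no true relation, P2, P3 and P5 agree within about 0.5 point in both models. With the true relation (distribution model, median 350) the set keeps 23, 22 and 20 of the 23 points. If the SR sample is kept and conversion after dosing is fast (mean 2 minutes), P2 sits 0.7–1.1 points below P3, which is why common time points are needed.

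**The case against.** The strongest reply has four parts.

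1. The endpoint as worded concerns subjects at or above 200, and P3 moves only about 0.4–4 points; P2 is a complementary row, and no P2–P3 test is planned. The sizes are right and the table is descriptive. But SAP 9.2.2.1 says the endpoint is reported as these eight percentages, P2 among them, and its layout invites the comparison.
2. The size, and in one scenario the sign, rests on assumptions: share converting early, their timing, spread of Cmax, and scaling from healthy volunteers. The proportional model ignores redistribution; under the distribution model a median subject with one stage keeps roughly 240–320 ng/mL and stays in P3. This stands. If every early converter still reaches 200, P2 does not change.
3. With 3–8 subjects in the low row, sampling error swamps the bias, and exact intervals are planned. True, but an interval does not show a bias with a known cause, and in a row this small one or two shortened-dose converters visibly move the estimate.
4. mITT is the protocol's efficacy population, and conversion by achieved Cmax under inhale-to-conversion is a legitimate description. Agreed, which is why the mITT table should stay. SAP section 14 also ties each table to a listing, so part of the request is nearly met already. The unseen PK/PD plan may contain a full-dose analysis.

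**Conclusion.** The concern holds. Read as exposure-response, P2–P8 in mITT are distorted, because conversion shortens the dose and only converters may have a short dose. P2 is generally too high and P3–P8 modestly too low. With 10–40% of converters converting across the dosing period, the false P2−P3 gap is 2–25 points and P3 alone moves about 0.4–4. With late conversions only, the gap is under 3 points and may reverse. A true relation is typically attenuated, and is hidden or reversed only if a large share converts during dosing.

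The mechanism follows from the documents; its size does not, because neither document reports how many subjects convert during dosing or their Cmax. That no full-dose version exists is established for the protocol and SAP only. This is a worthwhile correction to a descriptive table, held with medium confidence on size.

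**What to change.** - Keep the mITT table and add a footnote that dosing stops at conversion, so Cmax in early converters partly reflects the outcome.
- Add a P2–P8 sensitivity table in subjects who completed both inhalation stages and were still in AF at the end of dosing. Count conversions from then to 90 minutes after initiation.
- In that table take Cmax from the same scheduled samples for everyone (between inhalations and 1, 3, 10, 30, 60 and 90 minutes post dose), leaving out the extra SR sample.
- List converters during dosing separately, with dose received and Cmax.

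The cost is one footnote, one table and one listing from data already collected. The new table supplements the mITT estimate and does not replace it, because it drops the fastest responders. If a share f of converters converts during dosing, with overall rate p = 13/27, it keeps 1 − fp of mITT and its rate is (1 − f)p/(1 − fp). For f = 10, 25 and 40% that is 95, 88 and 81% of mITT, and a rate of about 45, 41 and 36% instead of 48%, with wider intervals.
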